10.13.10.2.2. Adverse Events and Serious Adverse Events

Adverse events will be reported by the participant (or, when appropriate, by a caregiver, surrogate, or the participant's legally acceptable representative) for the duration of the sub-study.

For further details on AEs and SAEs (Definitions and Classifications; Attribution Definitions; Severity Criteria; Special Reporting Situations; Procedures) as well as product quality complaints, refer to the main ApaRP protocol Section 8.3, Adverse Events and Serious Adverse Events, Section 10.4, Appendix 4, Adverse Events, Serious Adverse Events, Product Quality Complaints, and Other Safety Reporting: Definitions and Procedures for Recording, Evaluating, Follow-up, and Reporting.

10.13.11. Statistical Considerations

Statistical analysis will be done by the sponsor or under the authority of the sponsor.

The primary hypothesis of this sub-study is that coadministration of apalutamide 240 mg once daily with relugolix 120 mg once daily (following a loading dose of 360 mg) will achieve and maintain castrate levels of testosterone (<50 ng/dL). Clinical decision rule is that if 2 or more participants have a testosterone \geq 50 ng/dL on Day 28, the sub-study will be considered negative. The 95% 1-sided upper limit for the observed incidence of proportion of patients not able to maintain castrate levels is 22.1% if no participant out of 12 has a testosterone \geq 50 ng/dL. Percentage of participants maintaining testosterone <50 ng/dL through Day 28 will be summarized descriptively.

Once one cycle (28 days) of the coadministration of apalutamide and relugolix has completed, the participants will transition to the treatment schedule of the main ApaRP protocol beginning at Cycle 2 Day 1. Safety data collected during the coadministration of apalutamide and relugolix will be summarized descriptively. Data for participants transitioned to the main ApaRP protocol schedule will be summarized at the end of the study using methods similar to the main protocol analysis.

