- c Relugolix administered as 360 mg on first day of treatment (Day –14), followed by 120 mg on subsequent days.
- d If not occurring during an in-person visit, the study team should call the participant to ask about medication compliance.
- e Should be completed daily by the participant during sub-study treatment and provided to the study team at each sub-study visit (form located in Section 10.14, Appendix 14).
- f If participant's testosterone ≥50 ng/dL on Day 1 or Day 28, stop relugolix, switch to intramuscular ADT, and switch to main ApaRP study.
- g Focused examinations are generally limited to the body system or regions based on participant's self-assessment and AE reporting. Any new complaints, symptoms reported by participants or adverse events noted by providers should guide the need and extent of physical examination.
- h Collected at baseline, 12 months or end of treatment, and at 24 months or progression (whichever comes first) as part of the main ApaRP study.
- i Tissue sample to be collected and sent to sponsor's laboratory partner along with a copy of the full histopathology report of the specimen. See Section 8.6 for further details.
- j Collection of concomitant therapies does not begin until time of first dose of relugolix.
- k Collection of AEs does not begin until time of first dose of relugolix.

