10.13.5. Objectives and Endpoints

	Objectives		Endpoints
Pri	mary		
•	To assess if the addition of apalutamide to relugolix is able to maintain castrate levels of testosterone.	•	Percentage of participants maintaining testosterone <50 ng/dL through Day 28.
Sec	condary		
•	To evaluate the safety of coadministering apalutamide and relugolix at their indicated doses.	•	Adverse events through Day 28.

HYPOTHESIS

The primary hypothesis of this sub-study is that coadministration of apalutamide 240 mg once daily with relugolix 120 mg once daily (following a loading dose of 360 mg) will achieve and maintain castrate levels of testosterone (<50 ng/dL).

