10.13.6. SUB-Study Design

10.13.6.1. Overall Design

This is a single-arm, open-label, multi-center sub-study of apalutamide and relugolix in 12 participants with high risk localized prostate cancer who are treatment naïve, documented to have no evidence of metastatic disease prior to study entry, who are between Day 29 and Day 90 post-RP, whose PSA is ≤ 0.2 ng/mL at study entry, and who have recovered from surgery, per the

clinical judgment of the investigator. Upon completion of the sub-study, participants will be transitioned into the main ApaRP study protocol beginning at Cycle 2 Day 1.

The sub-study will be conducted in approximately 6 urology practices already conducting the main ApaRP study. There will be one study intervention group receiving relugolix monotherapy for 2 weeks followed by coadministration with apalutamide for 1 cycle (28 days). Treatment with relugolix will start following screening and completion of RP and no later than postoperative Day 90. Coadministration of apalutamide will start 14 days after initiation of relugolix monotherapy. Serum testosterone will be measured on Day -14 (ie, day of starting relugolix administration), Day 1 (ie, the day of starting coadministration with apalutamide), and Day 28. If a participant does not achieve a serum testosterone <50 ng/dL on Day 1 following 14 days of relugolix monotherapy, relugolix will be discontinued and the participant will switch to intramuscular ADT and the main ApaRP study and that participant will be replaced in the sub-study. If a participant achieves a serum testosterone <50 ng/dL on Day 1 following 14 days of relugolix monotherapy, coadministration with apalutamide will begin. As assessed on Day 28, if the coadministration of apalutamide and relugolix achieves and maintains a serum testosterone <50 ng/dL through Day 28 of the sub-study, participants will be given the opportunity to continue relugolix and apalutamide as part of the main ApaRP study. If the coadministration of apalutamide and relugolix does not achieve and maintain a testosterone <50 ng/dL through Day 28 of the sub-study in 2 or more participants, all participants on the sub-study will discontinue relugolix and switch to intramuscular ADT plus apalutamide as part of the main ApaRP study.

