The sub-study will have 12 participants. If 2 or more participants have a testosterone $\geq 50 \text{ ng/dL}$ on Day 28, the sub-study will be considered negative and all participants will switch to intramuscular ADT in the main ApaRP protocol. If 0 or 1 participant has a testosterone $\geq 50 \text{ ng/dL}$, the sub-study will continue until all 12 participants have been enrolled.

If a participant ends the sub-study early (ie, due to treatment non-compliance or not achieving a testosterone <50 ng/dL on Day 1 after relugolix monotherapy), that participant will be replaced in order to enroll 12 participants total. If the sub-study is terminated early due to lack of efficacy (ie, ≥ 2 participants have a testosterone $\geq 50 \text{ ng/dL}$ on Day 28) or safety (ie, ≥ 2 participants have prolonged QTc (\geq ULN) on Day 28), no further participants will be enrolled into the sub-study.

The timing and frequencies of study assessments are presented in the sub-study SoA (Section 10.13.3, Appendix 13). Efficacy assessments include serum testosterone and will be assessed at baseline (Day -14), after 14 days of relugolix monotherapy (Day 1), and after 28 days of coadministration of apalutamide and relugolix. A serum testosterone <50 ng/dL is considered castrate and the gold standard for indicating castration while on ADT. Study enrollment is defined as the day when the participant receives the first dose of relugolix monotherapy after having met all prescreening criteria. Adverse events will be assessed continuously from the time of enrollment and during treatment. A 12-lead electrocardiogram (ECG) will be conducted at screening, after 14 days of relugolix monotherapy, and after 28 days of apalutamide and relugolix coadministration, to examine QT prolongation. If any participant has a prolonged QTc at either Day 1 or Day 28, that participant will be removed from the study completely and replaced in the sub-study. If

2 participants have prolonged QTc at Day 28 the sub-study will terminated and any participants currently on the combination of relugolix and apalutamide will be evaluated for potentially changing to intramuscular ADT.

A diagram of the study design is provided in Section 10.13.2, Appendix 13, Schema.

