10.13.10.2. Safety Assessments

Participants will be monitored for safety from the beginning of the study treatment (Day -14) and at each sub-study visit. Events related to and associated with the recovery from the pre-planned RP will not be collected.

Adverse events will be reported and followed by the investigator as specified in the main ApaRP protocol Section 8.3, Adverse Events and Serious Adverse Events and Section 10.4, Appendix 4, Adverse Events, Serious Adverse Events, Product Quality Complaints, and Other Safety Reporting: Definitions and Procedures for Recording, Evaluating, Follow-up, and Reporting.

Any clinically relevant changes occurring during the sub-study must be recorded on the AE section of the eCRF.

Any clinically significant abnormalities persisting at the end of the sub-study/early withdrawal will be followed by the investigator until resolution or until a clinically stable condition is reached.

The sub-study will include the evaluations of safety and tolerability included in the main ApaRP protocol as noted in Section 8.2.1, Physical Examinations, and 8.2.2, Vital Signs.

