10.13.10.2.1. Electrocardiograms

A 12-lead ECG will be conducted at screening, after 14 days of relugolix monotherapy, and after 28 days of apalutamide and relugolix coadministration, to examine QT prolongation. During the collection of ECGs, participants should be in a quiet setting without distractions (eg, television,

cell phones). Participants should rest in a supine position for at least 5 minutes before ECG collection and should refrain from talking or moving arms or legs. If blood sampling or vital sign measurement is scheduled for the same time point as ECG recording, the procedures should be performed in the following order: ECG(s), vital signs, blood draw.

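### The sub-study safety summary begins at co-administration, so a man dosed with relugolix who leaves before his first apalutamide dose is in no defined summary

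*Protocol*

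**What the plan says.** Protocol 10.13.11 is the only statistical section for the sub-study; the SAP mentions neither relugolix nor the sub-study. It plans two summaries that bear on safety. The first is limited by period: "Safety data collected during the coadministration of apalutamide and relugolix will be summarized descriptively". The second covers men who transition to the main schedule, using methods similar to the main analysis.

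The secondary objective in 10.13.5 is "To evaluate the safety of coadministering apalutamide and relugolix at their indicated doses". The matching endpoint is adverse events through Day 28, with no start day and no analysis set.

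Collection and enrolment begin two weeks before co-administration:
- 10.13.3, footnote k: "Collection of AEs does not begin until time of first dose of relugolix".
- 10.13.10.2: "Participants will be monitored for safety from the beginning of the study treatment (Day -14) and at each sub-study visit".
- 10.13.6.1: "Study enrollment is defined as the day when the participant receives the first dose of relugolix monotherapy after having met all prescreening criteria".

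On QTc, 10.13.6.1 says of any man who has "prolonged QTc at either Day 1 or Day 28, that participant will be removed from the study completely and replaced in the sub-study". The same section stops the sub-study for QTc on Day 28 findings only.

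The Treated set (Protocol 9.3) and the safety analysis set (SAP section 4) each require one or more apalutamide doses.

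**The concern.** The planned summary is narrower than the exposure and the data collection. The men at issue are those who enrol, take relugolix, and leave without ever taking apalutamide. Some of them may leave for a safety reason, and they are replaced. A table restricted to co-administration would then describe only men who got through the first fortnight, with the replacements standing in for those who did not. In a 12-man sub-study, one omitted man is a visible share of the denominator.

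A secondary ambiguity concerns men who do transition. Protocol 9.4.5 counts events from the first study intervention. Section 2 defines that term as apalutamide plus ADT, and 10.13.8.1 describes relugolix as an ADT. SAP 5.1 and 5.6.2 instead count from the first dose of study drug, which 5.1 identifies as apalutamide. Whether their Day -14 to -1 events are summarised depends on which text is followed.

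**Working it through.** **The plan's own figure.** The one computed number in 10.13.11 is the one-sided 95% upper limit of 22.1% when 0 of 12 men fail. The exact limit is 1 − 0.05^(1/12) = 0.2209, so it reproduces. The present point does not depend on it, and the fix leaves it unchanged.

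**Time windows.** There is no Day 0 in the pill diary (10.14). Day -14 to -1 is 14 days and Day 1 to 28 is 28 days. The total of 42 matches the relugolix dosing period in 10.13.8.1. The share before co-administration is 14/42 = 33.3%. This is a share of dosing days, not of events or risk.

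**Which summary holds which man.**

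| Course | Co-administration summary | Transitioned men | Treated / SAP safety set |
|---|---|---|---|
| Completes Day 28 and transitions | Yes | Yes | Yes |
| Day 1 testosterone not castrate, switched to main study | No | Goes to main study | Yes, once on apalutamide |
| Prolonged QTc on Day 28 | Yes | No | Yes |
| Prolonged QTc on Day 1, apalutamide already taken | Any data after that dose | No | Yes |
| Prolonged QTc on Day 1, acted on before apalutamide | No | No | No |
| Leaves the study on relugolix alone (adverse event, seizure, death, withdrawal; 10.13.9.1, 10.13.9.3) | No | No | No |

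The last two rows are the gap. SAP 5.2 builds disposition on the safety set, so these men are not counted there either.

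**Order of events on Day 1.** Where an ECG and blood sampling fall at the same time point, "the procedures should be performed in the following order: ECG(s), vital signs, blood draw" applies (10.13.10.2.1). The testosterone result then gates apalutamide: "If a participant achieves a serum testosterone <50 ng/dL on Day 1 following 14 days of relugolix monotherapy, coadministration with apalutamide will begin" (10.13.6.1). So the ECG is very probably recorded before the first apalutamide dose. No text says it must be read and acted on first. The last row of the table does not depend on this order.

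**Effect on the table.** Let k men leave before apalutamide while 12 others start co-administration. The denominator moves from 12 to 12 + k, and the excluded men become visible as k/(12 + k):
- k = 1: 1/13 = 7.7%
- k = 2: 2/14 = 14.3%
- k = 3: 3/15 = 20.0%

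**How often.** The documents give no rate. For an assumed probability q that a man leaves before apalutamide, the chance of at least one such man before 12 reach co-administration is 1 − (1 − q)^12, and the expected number is 12q/(1 − q):

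| Assumed q | At least one | Expected number |
|---|---|---|
| 1% | 11.4% | 0.12 |
| 2% | 21.5% | 0.24 |
| 5% | 46.0% | 0.63 |
| 10% | 71.8% | 1.33 |
| 15% | 85.8% | 2.12 |

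These rows only show the range; none is an estimate for this sub-study.

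**The case against.** Four counter-arguments carry weight.

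- **The scope fits the objective.** The stated aim is the safety of the combination, and a man who never took apalutamide says nothing about it. This stands: the plan does not contradict itself, and the co-administration summary should be kept.
- **The endpoint could already reach back to Day -14.** It names an end day but no start day, and 10.13.11 does not say that nothing else will be summarised. This stands as a possible reading. It does not close the gap, because the endpoint names no analysis set and 10.13.11 is where the summaries are set out.
- **A separate specification may exist.** The synopsis says the sub-study will be analysed separately, so silence in the main SAP is weak evidence. The conclusion is therefore limited to the two documents supplied.
- **The Day 1 QTc case is contingent.** If the man takes apalutamide before his ECG is acted on, he is in the Treated set. This stands for that route, but not for exits during monotherapy.

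Three stronger inferences are tempting and unsupported. A reader might infer that the gap weakens the QTc stopping rule. It does not: that rule counts Day 28 findings, and a Day 1 finding leads only to individual removal. A reader might infer that safety data are lost. They are not: events and the reason for withdrawal are recorded (10.13.9.3, 10.13.10.2) and serious-event reporting applies. Lastly, the 98.7% testosterone suppression by Day 15 cited in 10.13.4.1 might seem to size the gap, since 1 − 0.987^12 = 14.5%. That figure concerns men who fail testosterone on Day 1. They switch to the main study and enter the safety sets there, so only their monotherapy-period events are in question.

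**Conclusion.** The point holds as a minor, inexpensive improvement. On the protocol and SAP as supplied, an enrolled, relugolix-dosed man who leaves before his first apalutamide dose is in no defined safety summary. For the Day 1 QTc route this assumes that the ECG is acted on before apalutamide is taken; for exits during monotherapy no such assumption is needed. It also assumes that 10.13.11 is read as written, without carrying the open-ended endpoint back to Day -14. The frequency cannot be derived from the documents. The consequence is confined to the sub-study safety counts and their denominator. The main study's primary result, the sub-study's testosterone decision rule and the stopping rules are unaffected.

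**What to change.** In 10.13.11, state that sub-study safety will be summarised from the first relugolix dose through Day 28 for all men who received any relugolix, including those later removed or replaced. Report the number removed for prolonged QTc at Day 1 and at Day 28 separately. Keep Day 1 to 28 co-administration as its own column so that the stated objective is still answered directly. This also settles whether Day -14 to -1 events are counted for men who transition.

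The cost is one or two sentences, using data already collected; SAP Appendix 2 remains open until database lock and could record the change. The downside is a slightly less favourable safety table, because a few more men and events may be counted. The removal, replacement and stopping rules stay as they are.

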10.14. Appendix 14: Sub-Study Pill Diary

1. Record the date, time, and the number of study medication tablets you took

2. Bring this pill diary to your clinic visits

INSTRUCTIONS:

*Day -14 ONLY: Take three tablets relugolix (360 mg) by mouth with or without food

Days -13 through -1: Take one tablet relugolix (120 mg) one time a day by mouth with or without food Days 1 through 28: Take one tablet relugolix (120 mg) AND four tablets apalutamide (240 mg) one time a day by mouth with or without food

Day	Date	Time	# of relugolix pills	# of apalutamide pills	NOTES (optional)			
-1	07/01/2021	09:00	1	0	This is an example.			
Take	Take ONLY relugolix Days -14 through -1							
-14*				0	Remember to take 3 relugolix tablets today ONLY			
-13				0				
-12				0				
-11				0				
-10				0				
-9				0				
-8				0				
-7				0				
-6				0				
-5				0				
-4				0				
-3				0				
-2				0				
-1				0				
There	is no break in	treatme	nt. Take relugolix Al	ND apalutamide Days 1	through 28			
1	07/15/2021	09:00	1	4	This is an example.			
1								
2								
3								
4								
5								
6								
7								
8								
9								
10								
11								
12								
13								
14								
15								

16			
17			
18			
19			
20			
21			
22			
23			
24			
25			
26			
27			
28			

10.15. Appendix 15: Protocol Amendment History

The Protocol Amendment Summary of Changes Table for the current amendment is located directly before the Table of Contents (TOC).

Amendment 1 (12 August 2020)

Overall Rationale for the Amendment: The main reason for the amendment is to add visit windows, administrative changes, and specify the unit for prostate-specific antigen (PSA) level for high risk population.

Section number	Description of Change	Brief Rationale		
and Name				
1.1 Synopsis Overall Design; 4.1 Overall Design; 4.4 End of Study Definition	Definition of end of study (EOS) is updated to: "The EOS is defined as the date of last participant's enrollment +24 months or discontinuation of all study participants from the study, whichever occurs first."	Clarified the definition of EOS to allow some participants to have follow-up visits beyond 24 months from enrollment.		
1.1 Synopsis Overall Design, Intervention Groups and Duration; 4.1 Overall Design; 6.1 Study Intervention Administration	Text is added to define treatment with apalutamide; text has been reworded to define treatment duration of 12 cycles for apalutamide.	To define treatment cycles and treatment duration.		
1.1 Synopsis Overall Design, Intervention Groups and Duration; 6.1 Study Intervention Administration	Text is added to mention the use of study intervention (apalutamide) as per its United States Package Insert (USPI).	Added text to accommodate prospective changes in apalutamide label.		
1.1 Synopsis Biomarker Evaluations; 8.6 Biomarkers	Text added to specify that full histopathology report will be sent along with the primary biopsy specimen to sponsor's laboratory partner.	To clarify the steps in biomarker assessment.		
1.3 Schedule of Activities (SoA)	Updated footnote j to: "Tissue sample to be collected from the primary biopsy and sent to sponsor's laboratory partner along with a copy of the full histopathology report of the biopsy specimen."			
1.2 Schema; 5.1 Inclusion criteria	Figure 1 and inclusion criterion 5 are updated to include the unit of PSA level as ng/mL.	Added the unit of PSA for clarity.		
1.3. Schedule of Activities (SoA)	'Focused physical examinations including skin assessment' is added at Baseline.	Text added to be consistent with Inclusion criterion 4 have recovered from radical prostatectomy (RP) procedure, per the clinical judgement of the investigator.		
1.3. Schedule of Activities (SoA) Appendix 3, 10.3.10 Source Documents	Footnote is updated to add recording of alcohol intake directly in the eCRF. Text to include history of alcohol intake including type, usage, amount, and frequency is added to the list of data that will be recorded directly into the electronic Case Report Form (eCRF).	Text added to record history of alcohol intake directly into the eCRF in alignment with lifestyle restrictions #1).		

Section number	Description of Change	Brief Rationale
and Name	Description of Change	Difer Rationale
1.3 Schedule of Activities (SoA)	New footnotes a and b are added to allow a visit window of ± 7 calendar days for Visits 2 through 8 and a visit window of ± 14 calendar days, Visit 9 onwards for all follow-up visits. The subsequent footnotes are rearranged alphabetically and are updated in the SoA.	Visit windows are added to allow scheduling flexibility.
1.3 Schedule of Activities (SoA)	New footnote i added for plasma samples: "Collected at baseline, 12 months or end of treatment, and at 24 months or progression (whichever comes first)."	Added to clarify the guidance of 'whichever comes first'
1.3. Schedule of Activities (SoA)	New footnotes k and l are added to start collection of concomitant therapies and adverse events (AEs) from the time of first dose of apalutamide.	Added the day of commencing concomitant therapy and AE collection to be consistent
8.3.1 Time Period and Frequency for Collecting AE and SAE Information; Appendix 4, 10.4.1 AE Definitions and Classifications	Reporting of AEs from the time after enrollment is changed to Reporting of AEs from the time after the participant receives the first dose of apalutamide.	throughout the protocol and in agreement with Global Medical Safety (GMS) to collect AEs beginning with dosing (and not to collect AEs that could be associated with RP).
8.3.1 Time Period and Frequency for Collecting AE and SAE Information	Text added to mention that AEs will additionally be monitored during phone calls with the participants.	To include all timepoints for AE monitoring.
5.2. Exclusion Criteria	Exclusion criterion 1 is updated to exclude presence of soft tissue/bone metastasis or metastasis in distant lymph nodes. Exclusion Criteria 9 is updated with "any of the following within 6 months prior to baseline" at the	To clarify the metastasis criterion. Rearranged the wording to clarify that the 6 months period applies to
7.1. Discontinuation of Study Intervention	Text is added to record the subsequent therapy, if known, in the eCRF for participants discontinuing the study intervention due to disease progression.	Added instructions to record subsequent therapy.
	Deleted the text: "Study intervention assigned to the participant who discontinued study intervention may not be assigned to another participant."	To disallow reassignment of study intervention as this is not relevant for an open-label study.
7.2.1 Withdrawal From the Use of Research Samples; Appendix 3, 10.3.1 Regulatory and Ethical Considerations	'Optional research sample' is changed to 'research sample' and the sentences are reworded accordingly.	The provision to keep research samples optional is deleted as this is not considered optional collection.
7.2.1 Withdrawal From the Use of Research Samples	Paragraph on "withdrawal from optional research samples while remaining in the main study" is deleted. Provision of separate Informed Consent Form	The paragraph is not applicable as the provision to keep research samples optional is deleted. Separate ICF is not applicable for
	(ICF) for optional research is deleted.	included in the main ICF.
8.3.8 Adverse Events of Special Interest	Added text: "For apalutamide, there are no non-serious AEs of special interest identified."	To provide background information on apalutamide AEs of special interest.

Section number Description of Change		Brief Rationale
and Name		
	"Rash is an AE of clinical interest" is changed to	Text is modified for consistency
	"Rash is an AE of special interest".	with the heading.
Appendix 4, 10.4.3	Text to grade AEs as per Common Terminology	Changed the AE grading criteria to
Severity Criteria	Criteria for Adverse Events (CTCAE) version 5.0	be consistent with the standard for
	is added.	oncology studies.
	Text to grade AEs into mild, moderate, and severe	
	is deleted.	
Appendix 10, 10.10	Added new bullet points to the 'Guide for	Added additional bullets for clarity
Phone Calls With	discussion during phone calls'	on guidance for phone calls.
Participants		
Throughout protocol	Minor grammatical, spelling, and formatting	Minor errors were noted.
_	changes are made.	

REFERENCES

- 1. American Red Cross http://www redcrossblood.org/donating-donating blood/eligibility requirements
